5. TREATMENT PLAN

5.1 STUDY PROCEDURES

PLACEBO-CONTROLLED PERIOD

Screening (maximum 30 days): The screening period begins once the informed consent is signed.

- Informed Consent
- Inclusion/ Exclusion
- Medical History/ Demographics
- Height, Weight, Body Mass Index (BMI) [BMI= weight (kg)/height (m2)]
- Concomitant Medications/treatments
- Provide subject copies of the patient take home diary, which will consist of NRS pain (worst moment, average & current) and itch (worst moment & average) assessments to be completed by patients daily.
- Lesion Counts (HiSCR), mHSS, HS-PGA, PGA-ISD, IHS4, Hurley Staging
- DLQI, HADS, PGI-c, PGI-s, EQ-5D-3L, HSSD, HiSQOL
- Physical Exam
- Electrocardiogram
- Vital Signs (blood pressure, pulse, oxygen saturation, respiratory rate and body temperature)
- Urinalysis: pH, protein, glucose and blood cells (RBCs and WBCs)
- Blood Draw:
 - o Chemistry panel: Albumin, Alkaline Phosphatase, ALT, AST, GGT,

Bicarbonate (CO2), Calcium, Chloride, Creatinine, Glucose, Potassium, Sodium, Total Bilirubin, Total Protein, Urea Nitrogen (BUN)

- Hematology Panel: Complete Blood Count (CBC) with differential and platelets
- Infectious disease panel: HIV antibody, Hepatitis C antibody, Hepatitis B panel (HBsAg, anti-HBc, anti-HBs), and interferon gamma release assay (IGRA) for TB
- Serum pregnancy test for WOCBP
- Inflammation Markers: CRP (C-Reactive Protein), ESR (Erythrocyte Sedimentation Rate)
- Randomization to study arm (once confirmed patient has passed screening requirements).

***Patients will be monitored at the study site at visits 1, 2, 3, 17, 18 & 19 (weeks 0, 1, 2, 16, 17 & 18) for a minimum of 30-minutes after study drug administration. Vital signs and AE assessments will be done at 30 minutes (+/- 10 minutes) post-injection. ***

Visit 1 (Week 0) (day 0, must occur within 30 days of signing informed consent):

- At least 45 minutes before injection: Remove syringe from refrigeration and lay flat; allow to warm to room temperature. Do not heat
- Pre-injection
 - Verify patient still meets inclusion/exclusion criteria
 - Height, Weight, Body Mass Index (BMI) [BMI= weight (kg)/height (m2)]
 - Patient Diary
 - Baseline Lesion Counts (for future HiSCR assessments), mHSS, HS-PGA, PGA-ISD, IHS4 and Hurley Staging
 - o DLQI, HADS, PGI-c, PGI-s, EQ-5D-3L, HSSD, HiSQOL
 - Physical Exam, Vital signs, Urine pregnancy
 - o Urinalysis
 - Blood draw for chemistry, hematology, inflammation markers, PK/ADA, IL-6,
 PD, biomarker and research analysis
- Bermekimab/placebo subcutaneous injections (To deliver a loading dose to subjects in the bermekimab groups while maintaining blinding, all subjects will receive two injections)
- Post-injection
 - Adverse event monitoring

- Concomitant medications/treatments
- Visit 2 (Week 1) (day 7 +/-3); Visit 4 (Week 3) (day 21 +/-3); Visit 6 (Week 5) (day 35 +/-3):
 - At least 45 minutes before injection: Remove syringe from refrigeration and lay flat; allow to warm to room temperature. Do not heat
 - Pre-injection
 - Patient Diary
 - HiSCR, mHSS, HS-PGA, PGA-ISD, IHS4 and Hurley Staging
 - DLQI, HADS, PGI-c, PGI-s, EQ-5D-3L, HSSD, HiSQOL
 - o Physical Exam, Vital signs, Urine pregnancy
 - Blood draw for PK/ADA, IL-6, PD, biomarker and research analysis
 - Bermekimab/placebo subcutaneous injections (To deliver a loading dose to subjects in the bermekimab groups while maintaining blinding, all subjects will receive two injections)
 - Post-injection
 - Adverse event monitoring
 - o Concomitant medications/treatments

Visit 3 (Week 2) (day 14 +/-3); Visit 5 (Week 4) (day 28 +/-3):

- *At least 45 minutes before injection*: Remove syringe from refrigeration and lay flat; allow to warm to room temperature. Do not heat
- Pre-injection
 - Patient Diary
 - Vital signs, Urine pregnancy
 - Blood draw for PK/ADA, IL-6, PD, biomarker and research analysis
- Bermekimab/placebo subcutaneous injection
- Post-injection
 - Adverse event monitoring
 - Concomitant medications/treatments

Visit 7 (Week 6) (day 42 +/-3); Visit 11 (Week 10) (day 70 +/-3); Visit 14 (Week 13) (day 91 +/-3); Visit 15 (Week 14) (day 98 +/-3); Visit 16 (Week 15) (day 105 +/-3):

- At least 45 minutes before injection: Remove syringe from refrigeration and lay flat; allow to warm to room temperature. Do not heat
- Pre-injection

- Patient Diary
- Vital signs, Urine pregnancy
- Bermekimab/placebo subcutaneous injection
- Post-injection
 - Adverse event monitoring
 - o Concomitant medications/treatments

Visit 8 (Week 7) (day 49 +/-3); Visit 10 (Week 9) (day 63 +/-3):

- *At least 45 minutes before injection*: Remove syringe from refrigeration and lay flat; allow to warm to room temperature. Do not heat
- Pre-injection
 - Patient Diary
 - o HiSCR, mHSS, HS-PGA, PGA-ISD, IHS4 and Hurley Staging
 - 0 DLQI, HADS, PGI-c, PGI-s, EQ-5D-3L, HSSD, HiSQOL
 - Physical Exam, Vital signs, Urine pregnancy
- Bermekimab/placebo subcutaneous injection
- Post-injection
 - Adverse event monitoring
 - Concomitant medications/treatments

Visit 9 (Week 8) (day 56 +/-3):

- At least 45 minutes before injection: Remove syringe from refrigeration and lay flat; allow to warm to room temperature. Do not heat
- Pre-injection
 - Patient Diary
 - Vital signs, Urine Pregnancy
 - Urinalysis
 - Blood draw for chemistry, hematology, inflammation markers, PK/ADA, IL-6, PD, biomarker and research analysis
- Bermekimab/placebo subcutaneous injection
- Post-injection
 - Adverse event monitoring
 - Concomitant medications/treatments

Visit 12 (Week 11) (day 77 +/-3):

- At least 45 minutes before injection: Remove syringe from refrigeration and lay flat; allow to warm to room temperature. Do not heat
- Pre-injection
 - Patient Diary
 - Physical Exam, Vital signs, Urine pregnancy
- Bermekimab/placebo subcutaneous injection
- Post-injection
 - Adverse event monitoring
 - o Concomitant medications/treatments

Visit 13 (Week 12) (day 84 +/-3):

- At least 45 minutes before injection: Remove syringe from refrigeration and lay flat; allow to warm to room temperature. Do not heat
- Pre-injection
 - Patient Diary
 - o HiSCR, mHSS, HS-PGA, PGA-ISD, IHS4 and Hurley Staging
 - o DLQI, HADS, PGI-c, PGI-s, EQ-5D-3L, HSSD, HiSQOL
 - Physical Exam, Vital signs, Urine pregnancy
 - Blood draw for chemistry, hematology, inflammation markers, PK/ADA, IL-6,
 PD, biomarker and research analysis
- Bermekimab/placebo subcutaneous injection
- Post-injection
 - Adverse event monitoring
 - Concomitant medications/treatments

BLINDED ACTIVE DOSING PERIOD

Visit 17 (Week 16) (day 112 +/-3):

- At least 45 minutes before injection: Remove syringe from refrigeration and lay flat; allow to warm to room temperature. Do not heat
- Pre-injection
 - o Patient Diary
 - o HiSCR, mHSS, HS-PGA, PGA-ISD, IHS4 and Hurley Staging
 - DLQI, HADS, PGI-c, PGI-s, EQ-5D-3L, HSSD, HiSQOL

- o Physical Exam, Vital signs, Urine pregnancy
- Blood draw for chemistry, hematology, inflammation markers, PK/ADA, IL-6,
 PD, biomarker and research analysis
- o Urinalysis
- Bermekimab/placebo subcutaneous injection
- Post-injection
 - Adverse event monitoring
 - Concomitant medications/treatments

Visit 18 (Week 17) (day 119 +/-3); Visit 19 (Week 18) (day 126 +/-3); Visit 20 (Week 19) (day 133 +/-3); Visit 22 (Week 21) (day 147 +/-3); Visit 23 (Week 22) (day 154 +/-3); Visit 24 (Week 23) (day 161 +/-3); Visit 26 (Week 25) (day 175 +/-3); Visit 27 (Week 26) (day 182 +/-3); Visit 28 (Week 27) (day 189 +/-3); Visit 30 (Week 29) (day 203 +/-3); Visit 31 (Week 30) (day 210 +/-3); Visit 32 (Week 31) (day 217 +/-3):

- *At least 45 minutes before injection*: Remove syringe from refrigeration and lay flat; allow to warm to room temperature. Do not heat
- Pre-injection
 - Patient Diary
 - Vital signs
 - Urine pregnancy
- Bermekimab/placebo subcutaneous injection
- Post-injection
 - Adverse event monitoring
 - o Concomitant medications/treatments

Visit 21 (Week 20) (day 140 +/-3); Visit 29 (Week 28) (day 196 +/-3):

- At least 45 minutes before injection: Remove syringe from refrigeration and lay flat; allow to warm to room temperature. Do not heat
- Pre-injection
 - Patient Diary
 - HiSCR, mHSS, HS-PGA, PGA-ISD and IHS4
 - o DLQI, HADS, PGI-c, PGI-s, EQ-5D-3L, HSSD, HiSQOL
 - Vital signs, Urine pregnancy
- Bermekimab/placebo subcutaneous injection
- Post-injection

- Adverse event monitoring
- Concomitant medications/treatments

Visit 25 (Week 24) (day 168 +/-3):

- At least 45 minutes before injection: Remove syringe from refrigeration and lay flat; allow to warm to room temperature. Do not heat
- Pre-injection
 - Patient Diary
 - HiSCR, mHSS, HS-PGA, PGA-ISD and IHS4
 - o DLQI, HADS, PGI-c, PGI-s, EQ-5D-3L, HSSD, HiSQOL
 - Vital signs, Urine pregnancy
 - o Urinalysis
 - Blood draw for chemistry, hematology, inflammation markers, PK/ADA, IL-6,
 PD, biomarker and research analysis
- Bermekimab/placebo subcutaneous injection
- Post-injection
 - Adverse event monitoring
 - Concomitant medications/treatments

Visit 33 (Week 32) (day 224 +/-3):

- Patient Diary
- HiSCR, mHSS, HS-PGA, PGA-ISD, IHS4 and Hurley Staging
- DLQI, HADS, PGI-c, PGI-s, EQ-5D-3L, HSSD, HiSQOL
- Physical Exam, Vital signs, Urine pregnancy
- Blood draw for chemistry, hematology, inflammation markers, PK/ADA, IL-6, PD, biomarker and research analysis
- Urinalysis
- Adverse event monitoring
- Concomitant medications/treatment

FOLLOW-UP PERIOD

Visit 34 (Week 36) (day 252 +/-3):

- HiSCR, mHSS, HS-PGA, PGA-ISD, IHS4 and Hurley Staging
- DLQI, HADS, PGI-c, PGI-s, EQ-5D-3L, HSSD, HiSQOL
- Physical Exam, Vital signs, Urine pregnancy

- Blood draw for chemistry, hematology, inflammation markers, PK/ADA, IL-6, PD, biomarker and research analysis
- Urinalysis
- Adverse event monitoring
- Concomitant medications/treatment

UNSCHEDULED VISIT (if applicable)

- Patient Diary
- HiSCR, mHSS, HS-PGA, PGA-ISD, IHS4 and Hurley Staging
- DLQI, HADS, PGI-c, PGI-s, EQ-5D-3L, HSSD, HiSQOL
- Physical Exam, Vital signs, Urine or Serum pregnancy
- Electrocardiogram
- Blood draw for infectious disease panel, chemistry, hematology, inflammation markers, PK/ADA, IL-6, PD, biomarker and research analysis
- Urinalysis
- Adverse event monitoring
- Concomitant medications/treatment

EARLY TERMINATION VISIT (if applicable)

- Patient Diary
- HiSCR, mHSS, HS-PGA, PGA-ISD, IHS4 and Hurley Staging
- DLQI, HADS, PGI-c, PGI-s, EQ-5D-3L, HSSD, HiSQOL
- Physical Exam, Vital signs, Serum pregnancy
- Blood draw for chemistry, hematology, inflammation markers, PK/ADA, IL-6, PD, biomarker and research analysis
- Urinalysis
- Adverse event monitoring
- Concomitant medications/treatment

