In order to maintain blinding, all patients will receive two injections at week 0 and 1, followed by weekly injections from weeks 2 to 31. Additionally, at least one qualified individual will be designated at each study site to perform all preparation and injection of the investigational product. The designated injector(s) should have no other contact with the participant during the study, should not discuss the participant's treatment with the participant, participant's caregiver, or other site personnel at any time, and will not be permitted to review the participant's medical records, questionnaires, or the electronic CRF prior to each injection. The designated injector(s) should be documented in the source documents at each visit.

Study treatment will be administered weekly in the clinic for 31 weeks with weekly office visits for 32 weeks. Patients will remain at the study site for a minimum of 30 minutes (+/- 10 minutes) after injections at weeks 0, 1, 2, 16, 17 and 18 injections for safety monitoring.

During the 32-week treatment period, patients will attend weekly clinical study visits. Clinical assessments, collection of samples for bermekimab concentrations, and safety testing will be performed at specified clinic visits. The primary endpoint data will be collected at week 12. After completion of the 36-week study period, data will be locked and analyzed for safety and efficacy endpoints for all arms. In addition to the analyses that will be performed following the formal database lock at the end of the study at Week 36, an additional database lock may be performed at Week 16, and interim analyses utilizing unblinded efficacy data available as the study progresses, may also be conducted to help plan potential future development activities. An internal interim analysis committee (IAC) will be established to review the interim data and formulate recommended decisions/actions. The IAC will consist of at least a clinician and a statistician (neither of whom are involved in study conduct or compound development), one of whom will chair the committee, and may also include other members as required by the nature of the IAs. Details will be provided in a separate IAC charter, which will define the organization and roles and responsibilities of the committee, possible

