2.6 METHOD OF ADMINISTRATION

Following two initial 800 mg loading doses of either bermekimab or placebo, patients in all arms will receive 400 mg of either bermekimab or placebo via subcutaneous injection administered weekly. Each injection should be administered at least one inch from previous injection sites.

* At least 45 minutes prior to injection, remove the pre-filled syringe from

refrigeration

Lay the syringe on a flat surface and let it naturally warm to room temperature before injection. It may also be warmed by holding in hand. Do not heat the syringe.

Materials

Bermekimab pre-filled syringe for injection, warmed to room temperature* Sterile alcohol wipes Band-aids, along with 2x2 gauze bandages and paper tape Latex-free gloves

Injection Site

Abdomen, at least 2 inches away from the belly button

(Note: avoid areas where the skin is burned, scarred, hardened, inflamed, swollen, or damaged).

Injection

- Put on gloves
- Wipe injection site clean with alcohol pads
- Raise a fold of skin between the thumb and forefinger and insert needle as illustrated
- Insert needle as illustrated in adjacent diagram
- Inject drug slowly
- Withdraw needle. Place band-aid over injection site if necessary (*Note: If bleeding occurs, hold pressure on the injection site for 90 seconds or until bleeding stops, and then apply gauze bandage secured by tape*).

***Investigator may, at their judgement, administer antihistamines/NSAIDs to prevent or treat injection site reaction. This must be captured in eCRF.

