3. STUDY DESIGN AND OBJECTIVES

This is a randomized, double-blind, placebo-controlled study to further establish the efficacy and safety and explore dose effects for bermekimab monotherapy in adults with moderate-to-severe HS. Approximately 50% of patients enrolled will have failed prior targeted biologic therapy(ies) and approximately 50% will be naïve to these forms of biologic therapy in each arm. Patients will be assessed for study eligibility at the initial screening visit after providing informed consent. Thirty days are allowed in the screening window to complete all screening procedures and randomize the subject. During the screening period, certain treatments will be washed out, as applicable, according to eligibility requirements. Patients who fail initially may be re-screened once based on the investigator discretion but only if inclusion criteria are met at time of rescreening.

The study is approximately 40 weeks (30 day screening period, 32-week treatment period and a 4-week follow-up period) for all subjects.

Patients who meet eligibility criteria at screening will be randomized in a 1:1:1 fashion to one of three treatment arms:

- Arm 1: 800 mg loading dose of bermekimab (2 x 400 mg SC injections) at weeks 0 and 1 followed by weekly (qw) subcutaneous (SC) injections of 400 mg bermekimab through week 31
- Arm 2: 800 mg loading dose of bermekimab (2 x 400 mg SC injections) at weeks 0 and 1 followed by subcutaneous (SC) injections of 400 mg bermekimab every other week (q2w) alternating with matching placebo q2w through week 31.
- Arm 3: 4mL loading dose of placebo (2 x 2mL SC injections) at weeks 0 and 1 followed by weekly placebo injections from weeks 2 through week 15. Patients in Arm 3 will begin to receive weekly (qw) blinded subcutaneous (SC) injections of 400 mg bermekimab beginning at week 16 through week 31.

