	⁶ Loading Doses: Treatment arm 1: 800 mg loading dose of bermekimab (2 x 400 mg SC injections) at weeks 0 and 1; Treatment arm 2: 800 mg loading dose of bermekimab (2 x 400 mg SC injections) at weeks 0 and 1; Arm 3: 800 mg loading dose of placebo (2 x 400 mg SC injections) at weeks 0 and 1; Arm 3: 800 mg loading dose of placebo (2 x 400 mg SC injections) at weeks 0 and 1; Arm 3: 800 mg loading dose of placebo (2 x 400 mg SC injections) at weeks 0 and 1; Arm 3: 800 mg loading dose of placebo (2 x 400 mg SC injections) at weeks 0 and 1; Arm 3: 800 mg loading dose of placebo (2 x 400 mg SC injections) at weeks 0 and 1; Arm 3: 800 mg loading dose of placebo (2 x 400 mg SC injections) at weeks 0 and 1; Arm 3: 800 mg loading dose of placebo (2 x 400 mg SC injections) at weeks 0 and 1; Arm 3: 800 mg loading dose of placebo (2 x 400 mg SC injections) at weeks 0 and 1; Arm 3: 800 mg loading dose of placebo (2 x 400 mg SC injections) at weeks 0 and 1; Arm 3: 800 mg loading dose of placebo (2 x 400 mg SC injections) at weeks 0 and 1; Arm 3: 800 mg loading dose of placebo (2 x 400 mg SC injections) at weeks 0 and 1; Arm 3: 800 mg loading dose of placebo (2 x 400 mg SC injections) at weeks 0 and 1; Arm 3: 800 mg loading dose of placebo (2 x 400 mg SC injections) at weeks 0 and 1; Arm 3: 800 mg loading dose of placebo (2 x 400 mg SC injections) at weeks 0 and 1; Arm 3: 800 mg loading dose of placebo (2 x 400 mg SC injections) at weeks 0 and 1; Arm 3: 800 mg loading dose of placebo (2 x 400 mg SC injections) at weeks 0 and 1; Arm 3: 800 mg loading dose of placebo (2 x 400 mg SC injections) at weeks 0 and 1; Arm 3: 800 mg loading dose of placebo (2 x 400 mg SC injections) at weeks 0 and 1; Arm 3: 800 mg loading dose of placebo (2 x 400 mg SC injections) at weeks 0 and 1; Arm 3: 800 mg loading dose of placebo (2 x 400 mg SC injections) at weeks 0 and 1; Arm 3: 800 mg loading dose of placebo (2 x 400 mg SC injections) at weeks 0 and 1; Arm 3: 800 mg loading dose of placebo (2 x 400 mg SC injections) at weeks 0 and 1; Arm 3: 800																	
or placebo (2 x 400 mg SC mjections) at weeks 0 and 1.																		

⁷ Patients in Arm 3 will begin to receive active bermekimab therapy from visit 17 (week 16). Patients in all arms will remain blinded through end of study.

Blinded Active Dosing Period

Study Procedure			Blinded Active Dosing Period													
Visit (V)	V18	V19	V20	V21	V22	V23	V24	V25	V26	V27	V28	V29	V30	V31	V32	V33

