## 1.2. Trial Design

This is a randomized, double-blind, placebo-controlled study to further establish the efficacy and safety and explore dose effects for bermekimab monotherapy in adults with moderate-to-severe HS. It is anticipated that approximately 50% of patients enrolled will have failed prior targeted biologic therapy(ies) and approximately 50% will be naïve to these forms of biologic therapy in each arm. Patients will be assessed for study eligibility at the initial screening visit after providing informed consent. Thirty days are allowed in the screening window to complete all screening procedures and randomize the participant. During the screening period, certain treatments will be washed out, as applicable, according to eligibility requirements. Patients who fail initially may be re-screened once based on the investigator discretion but only if inclusion criteria are met at time of re-screening.

The study is approximately 40 weeks (30-day screening period, 32-week treatment period and a 4-week follow-up period) for all participants.

A diagram of the study flow (Figure 1) is provided below. Approximately 150 patients who meet eligibility criteria at screening will be randomized in a 1:1:1 fashion to one of three treatment arms:

**Bermekimab 400 mg SC (qw) (Treatment Arm 1)**: 800 mg loading dose of bermekimab (2 x 400 mg SC injections) at weeks 0 and 1 followed by weekly (qw) subcutaneous (SC) injections of 400 mg bermekimab through week 31

**Bermekimab 400 mg SC (q2w) (Treatment Arm 2)**: 800 mg loading dose of bermekimab (2 x 400 mg SC injections) at weeks 0 and 1 followed by subcutaneous (SC) injections of 400 mg bermekimab every other week (q2w) alternating with matching placebo q2w through week 31.

**Placebo (Treatment Arm 3)**: 4mL loading dose of placebo (2 x 2mL SC injections) at weeks 0 and 1 followed by weekly placebo injections from week 2 through week 15. Patients in Arm 3 will begin to receive weekly (qw) blinded subcutaneous (SC) injections of 400 mg bermekimab beginning at week 16 through week 31.

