## 7.1.1.1. Data Handling Rules

Unless otherwise specified, the following data handling rules will apply to PK analyses:

- Participants will be analyzed according to the treatment groups that they actually received.
- All concentration summaries for a particular timepoint will include data obtained from treated participants at the timepoint of interest without imputing any missing data.
- A concentration not quantifiable (below the lower limit of quantification) will be treated as 0 in the summary statistics and shown as the lower limit of quantification (< LLOQ) in the data listings.
- The data from a participant who meets 1 of the following dosing deviation criteria (if applicable) will be excluded from the by-visit data analyses from that point onwards:
- Discontinue bermekimab administrations.
- Skipped a bermekimab administration.
- Received an incomplete/ incorrect dose (if applicable).
- Received an incorrect study agent (if applicable).
- Received an additional bermekimab dose.

In addition, if a participant has an administration outside of dosing windows (Table 2), the concentration data collected at and after that visit will be excluded from the by-visit data analyses. Additional exclusions for incongruous PK data to be implemented based on Janssen SOP-07948. All participants and samples excluded from the analysis will be clearly documented in the Clinical Study Report.

Visit	Window
Week 0 through Week 32	$\pm$ 3 days from scheduled visit day
Final Safety and Efficacy Follow-up visit	$\pm$ 7 days from scheduled visit day

Table 2:	Dosing Window
----------	---------------

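### Protocol 5.1 applies the two-injection loading instruction to Weeks 3 and 5, although the rest of the plan limits it to Weeks 0 and 1; a lesser gap is that the Week 4/8 rescue rule has no scheduled lesion count.

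*Protocol*

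**What the plan says.** **Dosing.** Protocol 5.1 gives a single procedure list for "Visit 2 (Week 1) (day 7 +/-3); Visit 4 (Week 3) (day 21 +/-3); Visit 6 (Week 5) (day 35 +/-3". Its injection line carries the note: "To deliver a loading dose to subjects in the bermekimab groups while maintaining blinding, all subjects will receive two injections". The same note stands in the Visit 1 list, where it belongs. The list for Visits 3 and 5 (Weeks 2 and 4) and the later lists call for a single injection and have no loading text.

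Elsewhere the rule is different:

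- Protocol synopsis, Protocol Section 3 and SAP 1.5.2: "all patients will receive two injections at week 0 and 1, followed by weekly injections from weeks 2 to 31".
- Protocol 5.2.1, calendar footnote 6: "Treatment arm 1: 800 mg loading dose of bermekimab (2 x 400 mg SC injections) at weeks 0 and 1", with matching statements for the other arms. In the dosing row the footnote mark sits on V1 and V2 only.
- SAP 1.2, for both bermekimab arms: "800 mg loading dose of bermekimab (2 x 400 mg SC injections) at weeks 0 and 1".
- Protocol 2.6, which names no weeks: "Following two initial 800 mg loading doses of either bermekimab or placebo, patients in all arms will receive 400 mg".

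**Rescue.** Protocol 2.11.2 allows minocycline or doxycycline if, at Week 4 or Week 8, the AN count is at least 150% of baseline. Neither Section 5.1 nor the 5.2.1 calendar lists a lesion count at either visit.

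**The concern.** Section 5.1 is the visit-by-visit instruction that a site works from, and neither document says whether it or the calendar prevails when they differ. A site that follows it as printed gives one more injection than planned at Week 3 and another at Week 5. At stake are the dose actually received in the bermekimab arms and, for the patients concerned, their later contribution to the PK summaries.

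The rescue gap is a separate and smaller matter. Eligibility for rescue rests on a count that the schedule does not require, so it cannot be checked against scheduled data. Protocol 10.5.3.1 counts a rescued patient as a non-responder from the start of rescue, so the decision to rescue should be traceable.

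**Working it through.** **1. Dose before the Week 12 assessment (doses at Weeks 0 to 11).** The plan states no cumulative dose, so it is built from the arm definitions in Protocol Section 3. The literal reading of 5.1 takes Weeks 3 and 5 as further 800 mg loads in both bermekimab arms, because the note says the two injections deliver a loading dose to those groups.

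*Arm 1*
- Planned: 2 × 800 + 10 × 400 = 5,600 mg.
- 5.1 as written: 4 × 800 + 8 × 400 = 6,400 mg. Increase 800/5,600 = 14.3%.
- If only one of the two visits is affected: 6,000 mg. Increase 400/5,600 = 7.1%.

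*Arm 2* ("400 mg bermekimab every other week (q2w) alternating with matching placebo q2w through week 31"; the text does not say whether even or odd weeks are active)
- Planned: Weeks 2 to 11 hold five active doses either way, so 2 × 800 + 5 × 400 = 3,600 mg.
- 5.1 as written, Weeks 3 and 5 being active weeks: 4 × 800 + 3 × 400 = 4,400 mg. Increase 800/3,600 = 22.2%.
- 5.1 as written, Weeks 3 and 5 being placebo weeks: 4 × 800 + 5 × 400 = 5,200 mg. Increase 1,600/3,600 = 44.4%.

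*Arm 3* receives only placebo until Week 16, so its bermekimab dose before Week 12 stays at zero.

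In every arm the injection count through Week 11 goes from 2 × 2 + 10 = 14 to 4 × 2 + 8 = 16.

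**2. PK summaries.** SAP 7.1.1.1 lists an additional bermekimab dose among the dosing deviations whose data "will be excluded from the by-visit data analyses from that point onwards". The calendars schedule 12 PK samples: Weeks 0, 1, 2, 3, 4, 5, 8, 12, 16, 24, 32 and 36. SAP 7.1.1 requires sampling before dosing. An extra dose at Week 3 therefore affects Weeks 4, 5, 8, 12, 16, 24, 32 and 36 (8 of 12); one at Week 5 only affects Weeks 8, 12, 16, 24, 32 and 36 (6 of 12). These are per-patient figures. They apply only if the site follows 5.1, the extra syringe is active and the event is classed as a deviation.

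**3. Rescue visits.** Post-baseline lesion counts through Week 16 fall at Weeks 1, 3, 5, 7, 9, 12 and 16, so neither of the two rescue visits has one. The ±3-day windows do not help:

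- Week 4 is days 25–31. The neighbouring count windows are days 18–24 (Week 3) and 32–38 (Week 5).
- Week 8 is days 53–59. The neighbouring count windows are days 46–52 (Week 7) and 60–66 (Week 9).

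No windows overlap.

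**4. Sample size.** The stated 42 per arm for 60% versus 30% reproduces (power 80.0%, chi-square without continuity correction). Neither part of this point touches it.

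**The case against.** The strongest reply is that the dosing text is a grouping slip with only one possible correction. Every other dosing statement agrees, including the administration section itself, and no text explains why a loading dose would be given at Week 3 or 5. Visits 2, 4 and 6 share the same assessments, which explains the shared list. This stands as far as intent goes. It does not make the printed instruction right, and an error in a dosing instruction should not be left for sites to resolve.

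One could also read the note as adding one syringe, active or placebo, to an unchanged scheduled syringe. Arm 2 would then receive 3,600 to 4,400 mg. That is an assumption about syringe content which the text does not make. The printed purpose is to deliver the loading dose, and the loading dose in Arm 2 is 800 mg.

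On PK, the reply is that the loss is conditional and confined to descriptive summaries. That is correct.

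On rescue, the reply is that the rule is permissive, that a site may count lesions when it considers rescue, and that HiSCR is among the unscheduled-visit procedures. All true, but those procedures are optional under the 5.2.2 footnote. SAP 5.4.3.2.1 does say that lesions are counted at each visit, yet SAP 1.2 has assessments follow the Schedules of Activities, so that sentence does not add a count at Week 4 or 8.

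**Conclusion.** The contradiction is real and should be fixed. Section 5.1 is wrong as written for Weeks 3 and 5. If it is followed at both visits, the dose before Week 12 rises by 14.3% in Arm 1 and by 22% or 44% in Arm 2. These figures assume literal compliance and an 800 mg active load in both bermekimab arms; the Arm 2 figure also depends on which weeks are active, which is not stated. The documents give no basis for saying how many sites would comply.

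A reader might infer that the Week 12 comparison is compromised. The documents do not support that. The intended schedule can be recovered from all the other text. The full analysis set is analysed by randomised group. The per-protocol set excludes patients for missed administrations, not for extra ones. The instruction also applies to every arm alike, so following it would not by itself reveal treatment.

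A reader might likewise infer that the rescue gap biases the primary endpoint. No such bias is shown. The protocol counts rescued patients as non-responders, whereas SAP 5.3.2 treats protocol-specified rescue as part of the regimen. That difference is a separate matter. The missing count is a minor scheduling gap.

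**What to change.** **Dosing.** In Protocol 5.1, restrict the two-injection text to Weeks 0 and 1. Give Visits 4 and 6 their own single-injection list that keeps their lesion counts, questionnaires, physical exam and blood draw. They cannot simply join the Visits 8 and 10 list, which has no blood draw.

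**Rescue.** Add an AN count at Weeks 4 and 8 to Section 5.1 and the 5.2.1 calendar, or require one at those visits only when rescue is being considered. Moving the trigger to Weeks 5 and 9 would add no counts but would delay rescue by one week, so that is the sponsor's clinical choice. Align SAP 5.4.3.2.1 by saying that lesions are counted at the scheduled visits.

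**Cost.** One protocol amendment under Section 11.3 covers both parts, plus one SAP sentence. Routine counts at Weeks 4 and 8 add 2 per patient, about 2 × 150 = 300 in all, at visits already attended; counting only when rescue is considered adds fewer. Sample size, power and the primary analysis do not change.
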